3. Explore the experiences of critical care survivors following COVID-19 infection during their recovery phase, including perceptions about the care received and support available to them, using semi-structured interviews. The central study team will conduct semi-structured interviews in a representative sample of 40 patients. (See Schedule of Events for additional information.)
4. Assess geographical differences in the availability and structure of follow-up services offered to patients with critical COVID-19 after hospital discharge.
5. Explore the factors influencing the involvement of study team members in the study.

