12	How soon after hospital discharge do you contact patients?	
 
Within a week
 
Within 2 weeks
 
Within a month
 
Within 2 months
 
Within 3 months
 
Other (please specify)
 

13	In addition to the ICU follow-up service, are there any alternative arrangements for follow-up for COVID-19 patients?	
 
Yes:
 
Respiratory team led
 
GP led
 
ID led
 
Other (please specify)
 
No
 

14	Which MDT professionals are part of your ICU follow-up clinic? (Please select all that apply)	
 
ICU consultant
 
Critical Care Nurse / Specialist Nurse
 
Physiotherapist
 
Psychologist
 
Dietician
 
Respiratory physician
 
Infectious Diseases physician
 
Other (Please specify)
 

15	Which patients do you invite to attend the ICU follow-up clinic?	
 
All patients admitted to the ICU
 
All patients treated on the ICU for 24hrs or longer
 
All patients treated on the ICU for 3 or 4 days or longer
 
Other (Please specify)
 

16	At what time points do you invite patients to the clinic for their first visit?	
 
3 months post ICU or hospital discharge
 
6 months post ICU or hospital discharge
 
Other (please specify)
 

17	If patients are invited to attend more than one follow-up clinic, please indicate all relevant times:	
 
3 months post ICU or hospital discharge
 
6 months post ICU or hospital discharge
 
12 months post ICU or hospital discharge
 
Other (please specify)
 

18	What tools are used to determine a patients' functional recovery? (Please select all that apply)	
 
SF-36 (any version)
 
HADS
 
Locally derived questionnaire
 
EQ-5D
 

		
 
PTSD screening tool (please specify)
 
Others (please specify)
 

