19	Does the clinic have pre-negotiated access to any of the following services (not simply referral letters), if they are not already integral to the ICU follow-up clinic? (Please select all that apply)	
 
Clinical psychologist
 
Occupational therapist
 
ENT
 
Physiotherapy
 
Urology/Sexual Health Medicine
 
Other (Please specify)
 

20	How is the follow-up clinic funded?	
 
Not funded
 
ICU budget
 
Primary Care Trust
 
Other (please specify)
 
Don't know
 

21	In your opinion, is there a reason for your ICU having no follow-up clinic? (Please select all that apply)	
 
Financial constraints
 
Lack of clinical need
 
Lack of current evidence of benefit
 
Other (please specify)
 
No
 

22	Please feel free to add any additional comments here:	

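### Q19 and Q18 of the follow-up services survey have no null answer, so a wholly blank reply cannot separate no pre-negotiated access, or no tool used, from a skipped item

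*Combined protocol and SAP*

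**What the plan says.** Exploratory outcome 4 (section 3.3) is to "Assess geographical differences in the availability and structure of follow-up services offered" to patients with critical COVID-19 after hospital discharge. The instrument is the survey in Appendix 8, sent to all UK intensive care units (section 5.2, Survey of Follow-up Services).

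Three items bear on this point:

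- **Q14**: "Which MDT professionals are part of your ICU follow-up clinic", select all that apply. The list includes psychologist and physiotherapist. It does not include occupational therapy, ENT or urology, but has a free-text other box.
- **Q18**: "What tools are used to determine a patients' functional recovery", select all that apply. The list is SF-36, HADS, a local questionnaire, EQ-5D, a PTSD screening tool and others. There is no null answer.
- **Q19**, whose stem opens: "Does the clinic have pre-negotiated access to any of the following services (not simply referral letters), if they are not already integral". Respondents select all that apply. The list is clinical psychologist, occupational therapist, ENT, physiotherapy, "Urology/Sexual Health Medicine" and other. There is no null answer.

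Neighbouring items do offer one: Q13 and Q21 include no, and Q20 includes not funded and don't know. The instructions ask respondents to answer everything, but do not say that a reply is forced. Section 3.5 gives no analysis for this survey, and no section says how an empty item will be coded.

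**The concern.** Absence of a service is the answer that planning of follow-up care most needs, and Q19 gives no direct way to state it. A clinic with pre-negotiated access to none of the listed services has nothing to tick. Unless it uses free text, it falls into the same group as non-respondents. Clinics that can be read as an explicit no for one service are those that ticked some other service, so the explicit negatives leave out the least-served clinics.

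Either simple coding of blanks then distorts the availability figure. Coding blanks as no access counts skippers as lacking the service. Coding them as missing drops clinics that truly have none. If the habit of skipping differs between regions, part of any geographical contrast reflects form-filling and not services. Q18 has the same gap for clinics that use no tool.

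**Working it through.** The plan gives no sample size, target or expected proportion for this survey, so there is no figure to reproduce. All percentages below are assumptions, chosen to show scale.

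**1. What Q14 and Q19 determine for the psychologist.** Each item has two features: psychologist ticked or not, and any other box ticked or not. That gives 2 × 2 × 2 × 2 = 16 reply patterns:

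| Reply | Patterns | Reading |
|---|---|---|
| Psychologist ticked in Q14 | 8 | integral |
| Psychologist ticked in Q19 only | 4 | pre-negotiated access |
| Only other boxes ticked, in both items | 1 | neither |
| Q19 wholly blank with Q14 answered elsewhere; Q14 blank with other Q19 boxes ticked; or both blank | 3 | undetermined |

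The total is 8 + 4 + 1 + 3 = 16. These are counts of patterns, not expected frequencies. The undetermined pattern that matters most is Q14 answered and Q19 wholly blank.

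**2. Blanks coded as no access (psychologist).** Assume 30% integral (known from Q14), 30% pre-negotiated and 40% neither, with Q14 answered and a proportion s of clinics skipping Q19 regardless of status. Only the pre-negotiated 30% can be misclassified.

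Apparent lack = 0.40 + 0.30 × s

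- s = 0.05: 0.40 + 0.015 = 0.415, excess 1.5 points
- s = 0.10: 0.40 + 0.030 = 0.430, excess 3 points
- s = 0.20: 0.40 + 0.060 = 0.460, excess 6 points

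Two regions with identical services, one skipping 20% and the other 5%, differ by 0.460 − 0.415 = 4.5 points.

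**3. Bounds and coding as missing (psychologist).** Take a different assumed set of replies from 100 clinics: 30 tick psychologist in Q14, a further 20 tick it in Q19, and 50 tick it in neither. Of those 50, b leave Q19 wholly blank. The number lacking access lies between 50 − b (every blank is a skipper with access) and 50 (every blank is a true none). Treating blanks as missing gives (50 − b) / (100 − b).

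| b | Bounds, of 100 | Blanks as missing |
|---|---|---|
| 5 | 45 to 50 | 45/95 = 47.4% |
| 15 | 35 to 50 | 35/85 = 41.2% |
| 25 | 25 to 50 | 25/75 = 33.3% |
| 40 | 10 to 50 | 10/60 = 16.7% |

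If all the blanks are true nones, the correct figure is 50% in every row, and coding as missing understates it.

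**4. Occupational therapy, ENT and urology.** Q14 has no box for these, so an unticked box is ambiguous even when the rest of Q19 is answered. With assumed shares of 40% none, 20% integral and 40% pre-negotiated, the box is unticked by 40% + 20% = 60% of clinics before any skipping. That is 20 points above the true 40%, unless the Q14 free text captures the integral services.

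**The case against.** The strongest reply is that most of the information is already collected. Q14 identifies an integral psychologist or physiotherapist. A clinic that ticks any other Q19 box has answered the item and can be read as having no pre-negotiated psychologist. The other box and the closing comments item (Q22) allow a respondent to write none. Respondents are asked to answer every question, and the online build may force a reply, which the documents do not show. Section 5.5, although written for participant data, says unobtainable data will be reported as missing, so coding blanks as absence is not the stated plan. The objective is one of five exploratory ones, in a study described as descriptive.

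Much of this stands, and it limits the point. A reader might infer that lack of a psychologist cannot be counted at all; Q14 and Q19 together contradict that. A reader might also take a blank or negative Q19 to mean that survivors cannot get psychological care. It does not, because the item covers pre-negotiated access only and expressly leaves out ordinary referral letters. Nor is the word functional in the Q18 stem a real fault, since HADS and a PTSD tool are listed there by name; rewording it is a matter of preference.

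What the reply does not remove is the wholly blank item. Free text depends on the respondent volunteering it. Forcing a reply without a null box would push a clinic with no access into an untrue tick or into the other box. Reporting blanks as missing drops true negatives.

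**Conclusion.** The point holds in a limited form. A wholly blank Q19 or Q18 cannot separate a true none from non-response, and clinics with no listed access always give that reply unless they use free text. For psychologist and physiotherapist, lack of pre-negotiated access can be counted where Q14 and Q19 are both answered, and bounded otherwise. For occupational therapy, ENT and urology, integral provision is also unrecoverable except through Q14 free text.

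Under the assumed 30/30/40 split, with blanks coded as no access, the overstatement for the psychologist is about 1.5 to 6 points for skip rates of 5% to 20%, and the false regional gap is about 4.5 points. Those sizes rest on the assumed shares, on skipping unrelated to access, and on a coding rule that the plan does not state. The primary patient-level outcomes are unaffected. This is a minor, worthwhile improvement to the form.

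**What to change.** - **Q19**: add none of these and don't know, and an already-part-of-the-clinic answer for each service. One row per service would do this cleanly.
- **Q18**: add no tool used and don't know.
- **Analysis**: derive psychologist and physiotherapist access from Q14 and Q19 together. Count only explicit negatives as absence. Report remaining blanks as missing, by region.

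The cost is a minor amendment to the survey form, which section 7.7 routes through the Chief Investigator, the REC and local sites, and a check that the ten-minute completion estimate still holds. If the survey is already out, replies to the old form should be flagged by version. Units with a wholly blank Q19 or Q18 should be queried, or their results reported as bounds as in step 3 of the working.

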## Appendix 9: Study Team Survey

The PIM-COVID study is the first trainee-led study facilitated by the Trainee Research in Intensive Care (TRIC) Network. We are interested in your feedback on the study and finding out about your views on research. The results will be analysed and interpreted for future presentation and publication and will inform future activities of the TRIC network.

You have been asked to participate as you were a contributor to the PIM-COVID study. The survey will take you about five minutes to complete. Your responses will be stored confidentially and securely for 10 years.

For further information please contact [[contact]](mailto:[contact]).

### **DEMOGRAPHICS**

**We would like to know a little bit more about the demographics and previous research experiences of those involved in the PIM-COVID study teams.**

#### **Question 1**

##### **What is your role?**

*(Please select one option from the list below)*

- |  |                          |
|--|--------------------------|
| Foundation trainee                                     |  |
| Core trainee   |  |
| Specialist Registrar                                   |  |
| Junior doctor not in training                          |  |
| Consultant   |  |
| Research nurse   |  |
| Advanced critical care practitioner                    |  |
| Psychologist   |  |
| Allied healthcare professional (please specify) |  |
| <hr/>  |                          |
| Other (please specify)                          |  |
| <hr/>  |                          |

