**Question 4**

**Are you currently employed in, or have previously been employed in, a position with protected research time as part of your job plan?**

*(Please select all that apply)*

- | If yes:                                      | Current role             | Previous role            |
|---|--------------------------|--------------------------|
| Academic Foundation Programme                       |  |  |
| Academic Clinical Fellow                            |  |  |
| Academic Clinical Lecturer                          |  |  |
| Research Fellow                                     |  |  |
| Associate Principal Investigator (of another study) |  |  |
| Principal Investigator (of another study)           |  |  |

*If no:*

- |   |                          |
|---|--------------------------|
| No previous research experience   |  |
| Previous research experience but in my own time whilst not employed in a research role (i.e. recruiting patients, data collection, research publication, research presentation) |  |
| Other (please specify)  |  |
| <hr/>   |                          |

---

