### **Question 6**

**What role did you have on the PIM-COVID delegation log?**

*(Please select one)*

- |                                    |                          |
|------------------------------------|--------------------------|
| Trainee PI                         |  |
| Senior PI                          |  |
| Sub-investigator / co-investigator |  |
| Not sure                           |  |

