**Question 13**

**If you stopped your involvement in the PIM-COVID study what was the reason?**  
*(Please select all that apply)*

- |  |                          |
|--|--------------------------|
| Moved to a different job or department |  |
| Demands on time or other commitments   |  |
| Did not want to continue               |  |
| Site stopped collecting data           |  |
| Other (please specify)                 |  |

Questions 14-24 are for junior doctors and allied health professionals only (not research nurses or Consultants), as indicated in Question 1.

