**Question 16**

**Did any of the following concerns or barriers impact your ability to undertake work on PIM-COVID?**

	Strongly disagree	Disagree	Neither agree nor disagree	Agree	Strongly agree
Lack of protected research time					
Already involved in other research projects					
Other non-clinical commitments (i.e. exams, quality improvement, teaching)					
Other clinical commitments					
No previous research experience					
Only based in department for a limited amount of time (e.g. trainee rotation)					
Lack of academic culture at my local site					

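### Question 1 of the study team survey has no reference date, yet it alone records grade and decides who is asked Questions 14 to 24

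*Combined protocol and SAP*

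**What the plan says.** Appendix 9 is a feedback survey of team members and serves exploratory objective 5 (section 3.2). Its introduction addresses people who have already done the work: "You have been asked to participate as you were a contributor to the PIM-COVID study".

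Question 1 then asks "What is your role", with the instruction "Please select one option from the list below". Three trainee grades (foundation, core, specialist registrar), junior doctor not in training, consultant, research nurse and several other professions are listed as alternatives.

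The note after Question 13 sets the routing: "Questions 14-24 are for junior doctors and allied health professionals only (not research nurses or Consultants), as indicated in Question 1".

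Two other items bear on role or post. Question 6 asks "What role did you have on the PIM-COVID delegation log". Question 4 asks about current and previous posts, but only those with protected research time.

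The survey allows for job changes. A reason offered in Question 13 for stopping involvement is "Moved to a different job or department", and Question 16 lists a time-limited placement, with trainee rotation as its example, among the possible barriers. The Study Summary gives a study duration of 24 months.

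**The concern.** A question that both classifies respondents and drives skip logic needs a stated time basis. Without one, two people with the same history can give different answers, and here the answer determines which questions they see.

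The block at stake is introduced as an attempt to learn what influences trainees and allied health staff to take part in research. A registrar who worked on the study and has since become a consultant belongs to that target group for the period being asked about. If this person reads Question 1 as the role held today, the routing treats them as outside the group. Their answers on why they joined, what hindered them, how the work fitted around clinical duties and what they learned are never collected. No analysis can recover them afterwards. The people lost in this way are those who were closest to consultancy, so the loss depends on seniority.

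**Working it through.** The plan gives no figure on this point, so there is nothing to reproduce. The check is a trace of the questionnaire's logic.

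**Step 1. Time basis of each item.**

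| Item | Time basis | Records grade? | Routes Questions 14 to 24? |
|---|---|---|---|
| Question 1 (role) | Present tense, not tied to the study | Yes | Yes, alone |
| Question 4 (protected research posts) | Current and previous | No | No |
| Question 6 (delegation-log role) | Past, tied to the study | No: trainee PI, senior PI, sub- or co-investigator, not sure | No |
| Question 10 (who ran the study at the site) | Past | No: describes the site, not the respondent | No |
| Question 13 (reason for stopping) | Past | No | No |

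The only item that records grade is also the only one that routes, and it has no date. The authors did tie the neighbouring role item, Question 6, to the study.

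**Step 2. One respondent traced through.** Take a specialist registrar during the study who is a consultant when the survey arrives.

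- *Question 1 read as role now:* the answer is consultant, and the note after Question 13 excludes this person from Questions 14 to 24. No later item brings them back.
- *Question 1 read as role on the study:* the answer is specialist registrar, and Questions 14 to 24 are asked.

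The same career gives two different data records, depending on how an undated question is read.

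**Step 3. What the first reading loses.**

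- Questions 14 and 15: reasons for joining and hopes for the work. Past.
- Questions 16 and 17: barriers and concerns. Past.
- Question 18: fit with clinical commitments and working hours. Past.
- Questions 19 and 20: administering questionnaires by telephone. Mainly past.
- Question 21: what was learned. Past.
- Questions 22 to 24: career intentions, future involvement and present views. Present or future.

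Questions 14 to 21 thus concern the time of the study work, and study-time role is the natural basis for routing them. For Questions 22 to 24 that is not clear.

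**Step 4. Can Question 6 repair it?** Only in part. A respondent who ticks consultant in Question 1 and trainee PI in Question 6 can be recognised as a former trainee, but by then the answers to Questions 14 to 24 are already missing. A former trainee who was a sub- or co-investigator cannot be recognised from Question 6.

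**Step 5. Who is affected.** A move between trainee grades can misstate grade but leaves routing unchanged. A move from trainee to consultant changes both, if Question 1 is read as role now. Someone whose grade has not changed is unaffected under either reading.

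**The case against.** The strongest reply is that Question 1 does not say current role. It comes straight after an introduction addressed to study contributors, under a heading about the people in the study teams, so a respondent could well give the grade held on the study. This stands as far as it goes: the documents do not show that every promoted trainee will be classed as a consultant. It does not remove the problem, because some will read the question one way and some the other, and nothing in the survey settles which is meant.

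The second reply is that much is still collected from anyone routed out. This also stands. Questions 2 to 13 are not restricted by role, and weekly hours (Question 11) are asked of everyone. A reader might infer that time burden is lost altogether, but only the further time items in Question 18 are.

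The third reply concerns Question 4. A reader might infer that its current and previous columns share the fault, because they cannot show whether protected time was held during the study and so cannot be matched to the protected-time item in Question 16. The documents do not support treating this as a defect. No such match is planned, Question 4 serves the topic of previous academic experience (section 5.2), it does not route, and Question 16 asks directly whether lack of protected time affected the work.

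The last reply is about importance: this is a five-minute feedback survey for one exploratory objective. That is correct, and it limits the weight of the point.

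**Conclusion.** The point holds in a limited form. Question 1 has no reference date, so grade may be defined differently from one respondent to the next. A former trainee who is now a consultant and answers literally misses Questions 14 to 21, which concern their time as a trainee, and Questions 22 to 24 as well.

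The number affected cannot be computed. The documents give no count of team members by grade and no promotion rate, and the text available gives no survey date.

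A reader might be tempted to put a percentage on it. If a fraction p of registrars became consultants each year and the survey came t years after the work, the share promoted would be 1 − (1 − p)^t. Assuming p = 0.10 and t = 0.5 gives 1 − 0.90^0.5 = 5.1%; assuming p = 0.20 and t = 2 gives 1 − 0.80^2 = 36%. Neither p nor t comes from the documents. The lower end should be 0%, because Question 12 allows for involvement that is still ongoing, and section 3.6 of a protocol dated April 2022 plans recruitment to as late as September 2022. The upper end needs both extremes at once, applies only to former registrars, and assumes that all of them read Question 1 as role now. These figures are an illustration, not an estimate.

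The effect is confined to exploratory objective 5. The HADS and IES-6 outcomes and all other patient data are untouched. The change is still worth making, because it costs almost nothing and the skipped answers cannot be recovered later.

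**What to change.** Reword Question 1 to: *What was your role when you worked on PIM-COVID? (if more than one, the role held longest)*. Route at least Questions 14 to 21 on that answer.

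For Questions 22 to 24, state whether study-time role or current role decides who is asked. If current role is chosen, add a one-line item recording it. Question 4 needs no change.

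The cost is one reworded question, a revised routing note, slight recall error among those who changed post during the study, and at most one extra item.
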